1.7 Data Collection

A. Primary Data Collection

- **Location:** Data will be collected during physical therapy visits at the UOA research sites (Wall, Somerset, Avenel, Morganville).
- **Process of Data Collection:** Data will be collected by the specified team members. The data collection process involves administering the Tampa Scale of Kinesiophobia (TSK) to assess pre-operative and post-operative kinesiophobia levels at 3, 6, and 12 months following ACL reconstruction. Single-leg balance performance is evaluated through three trials with a step in between at the same intervals, measuring time-to-touchdown. Strength measurements, including quadriceps and hamstrings strength at a 90-degree joint angle, as well as hip flexion, hip extension at full extension, and hip adduction strength, are recorded using the MicroFET device. At 6 months, a physical therapist conducts a functional evaluation, encompassing the Single-Leg Hop Test, Triple Hop Test, Triple Crossover Test, and a timed 20m Hop on a Single Leg. All data collection will be done directly on REDCap.
- **Timing and Frequency:**

The study duration spans 1-2 years, with the following timeline:

 1. Pre-operative Assessments:
 - a. Initial participant recruitment and baseline assessments occur before ACL reconstruction surgery. Including PROMs (TSK, KOOS, PROMIS-10) -part of Standard of Care.
 2. Post-operative Assessments:
 - a. Tampa Scale of Kinesiophobia (TSK) are conducted at 3, 6, & 12 months post-operatively.
 3. Functional Evaluation:
 - a. A physical therapist will conduct a single leg balance test at 3 & 6 months.
 - b. PT will also conduct a comprehensive assessment at 6 months post-operatively, involving the Single-Leg Hop Test, Triple Hop Test, Triple Crossover Test, and Timed 20m Hop on a Single Leg. (This is part of standard of care)
 4. Data Analysis:
 - a. Initiated upon the completion of data collection.
 5. Reporting and Publication:

a. Findings and conclusions are compiled and prepared for reporting and potential publication.

▪ **Study Instruments:**

- microFET 2 dynamometer
 - FDA Class II device
 - A handheld device that is used to measure muscle strength
 - The flat sensor is placed on the muscle group to be tested, and then the subject flexes against the resistance of the device held against their limb
 - Device will record force in kilograms or pounds
- Tampa Scale of Kinesiophobia
 - A validated tool to measure the degree of kinesiophobia in participants
- Functional Evaluation Tools:
 - Single Leg balance test
 - Single-Leg Hop test
 - Triple Hop Test
 - Triple Crossover test
 - Timed 20m hop on a single leg
- Intake Form
 - Form to be completed after enrollment to study
 - Will record subject identifiers (listed below), date of surgery, and gender

▪ **Subject Identifiers:**

- Participants will be assigned a study number and no personal identifiers will be utilized.
-

1.8 Timetable/Schedule of Events

- Tentative Schedule:

- Subjects are enrolled pre-surgically by physical therapist during pre-operative therapy.
- Pre-Operative PROMS will be collected prior to surgery. They will be delivered by text or email.
- Post-operative PROMS will be completed at 3 months, 6 months, 1 year.
- Single leg balance testing will be completed by physical therapists at 3 months, 6 months
- Functional testing will be completed by physical therapists at 6 months.
- At 1 year post-op, the patients will complete PROMS.

2.2 Research Staff Training

All team members have been CITI certified, hold appropriate state licensing of credential.

2.3 Other Resources

All therapy equipment, space, and computers for data recording will be provided by UOA.

3.0 Multi-Center Research

NA

4.0 Subject Considerations

4.1 Subject Selection and Enrollment Considerations

A. Method to Identify Potential Subjects

Potential subjects will be identified by their attending surgeon.

B. Recruitment Details

A physical therapist will meet with the patient after being notified by the surgeon of a potential subject. They will explain the purpose of the study and what it entails. They will be given the benefits and risks of the study as well as alternatives to not enrolling. The written consent form will be explained to them. They will have appropriate time to consider enrolling in the study.

C. Subject Screening

Team members will talk through the inclusion and exclusion criteria with the subject.

▪ Inclusion Criteria

Patients 18 years and older with a confirmed ACL tear on MRI scan

▪ Exclusion Criteria

Elderly patients, prior history of ACL tear, patients with other pre-existing physical conditions in which single-leg balance would put them at risk of harm

D. Privacy Protections

All data entry and collection forms will be destroyed by shredding once data is transcribed onto REDCap. Access to this is password-protected and limited to only the study team.

4.3 Number of Subjects

A. Total Number of Subjects

25 subjects will be accrued. This will be the number of subjects needed to complete the research procedures. We expect to inflate this number by 10% in the recruitment process to account for drop-out.

B. Total Number of Subjects If Multicenter Study

Total number of subjects across all sites will be at least 25.

C. Feasibility

Recruiting 25 patients for this study will be feasible given that each clinic sees roughly [NUMBER] of first-time ACL tear patients each month. We expect to be able to recruit 25 patients within [# OF MONTHS]

4.4 Consent Procedures

A. Consent Process

▪ Location of Consent Process

- UOA Somerset
- Morganville
- UOA Wall
- UOA Avenel

▪ Ongoing Consent

Patients will be reminded that they may reach out to any of the investigators with questions or concerns.

▪ Individual Roles for Researchers Involved in Consent

The physical therapists will be responsible for obtaining consent for potential subjects. They will be notified by the attending surgeons who will screen patients regarding potential subjects for the study. At this time eligibility will be determined per the inclusion and exclusion criteria. Study team members will explain the purpose of the study, why the potential subject is being chosen for screening, what kind of time commitment and study activities the subject would be asked to participate in, potential risks and benefits associated with participating in the study, and what their alternative options are to joining the study.

▪ Consent Discussion Duration

15 minutes

▪ Coercion or Undue Influence

The primary surgeon caring the subject will not be a part of the consenting process to avoid undue pressure to join the study. Physical therapists will discuss the study with potential subjects and inform them that their alternative to joining the study is to decline participation which not affect their care.

▪ Subject Understanding

To ensure adequate understanding of the study, patients will be encouraged to ask questions about aspects they do not understand and the person obtaining consent will employ teach back methods to ensure patient understanding.

▪ Protecting Privacy

Consent discussion will occur in a private room with only the patient and the consenting individual present.

B. Documentation of Consent

▪ Documenting Consent

The consenting person will document consent in ordinance with the IRB requirements as stated in the Toolkit form. The patient will sign the consent form which will then be included in the visit note for the patient. A copy of the signed consent form will be provided to the patient, and it will be scanned into their medical record.

4.5 Economic Burden and/or Compensation for Subjects

A. Expenses

There are no expenses for the patient beyond regularly incurred cost for physical therapy.

B. Compensation/Incentives

Patients will voluntarily participate in this study. There will be NO patient compensation for participation in this study.

C Compensation Documentation

NA

4.6 Risks of Harm/Potential for Benefits to Subjects

A. Description of Risks of Harm to Subjects

▪ Reasonably Foreseeable Risks of Harm

▪ There is no foreseeable risk of harm from participation in this study. It possess minimal risk to the patient beyond the real of normal post-operative physical therapy. Since all data collection will be de-identified, there is minimal risk of release of personal information.

▪ Risk of Harm from an Intervention on a Subject with an Existing Condition

Psychological conditions including fear/anxiety will be assessed via the TSK (PROM) and patient concerned directly addressed by the physical therapists or referred for professional care.

▪ Observation and Sensitive Information

NA

B. Minimizing Risks of Harm

There is no more than minimal risk of harm associated with participation in this study.

▪ Certificate of Confidentiality

NA

▪ Provisions to Protect the Privacy Interests of Subjects

PROMS will be completed online on a secure server. Functional assessment of balance/function will be recorded onto a recording sheet with only patient number and no personal identifiers.

C. Potential Direct Benefits to Subjects

Participation in this study provides minimal personal benefits, but does help to advance the understanding of the impact of kinesiophobia on ACLR recovery and function.

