1.0 Research Design

1.1 Purpose/Specific Aims

The purpose of the research is to investigate the relationship between TSK scores and single-leg balance test results in ACL reconstruction patients.

A. Objectives

This study aims to answer the following questions:

- 1.) Is there a significant difference in single-leg balance between those with kinesiophobia and those without?
- 2.) Is there a change in kinesiophobia and single-leg balance test results over time?

B. Hypotheses / Research Question(s)

This study's hypothesis is that patients who score higher on the TSK (more fear) will do worse on the single-leg balance test than patients who score lower on the TSK.

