1.3 Research Design and Methods

This study is a randomized prospective study.

A. Research Procedures

The research procedures for this project will involve a comprehensive assessment of kinesiophobia using the Tampa Scale of Kinesiophobia (TSK) at both pre-operative and post-operative time points, specifically at 3 months, 6 months, and 1 year after ACL reconstruction. This will provide insights into the evolution of kinesiophobia throughout the critical phases of recovery. Additionally, the study aims to investigate the relationship between kinesiophobia and single-leg balance. The single-leg balance tests will be conducted in a trial of three, with a step in between each trial, to ensure a robust evaluation of participants' balance abilities. The time taken to touchdown during the single-leg balance tests will be measured. These assessments will be performed at 3 months, 6 months, 9 months, and 1 year post-operatively. Importantly, the balance assessments will be conducted on both the right and

left sides, allowing for a detailed comparison and analysis of potential asymmetries in balance recovery between the two limbs.

At the 6-month mark, all participants will undergo a functional evaluation by a physical therapist, including a single-leg hop test, triple hop test, triple cross-over test, and a timed 20m hop on a single leg. These functional tests are designed to provide additional insights into the participants' overall recovery and functional capabilities. Furthermore, strength testing will be conducted using the MicroFET device, with a focus on quadriceps and hamstrings at a 90-degree joint angle, as well as assessments of hip flexion, hip extension at full extension, and hip adduction. This comprehensive grouping of assessments at the 6-month milestone will contribute valuable data to the study, enhancing our understanding of the interrelationships between kinesiophobia, single-leg balance, functional performance, and muscle strength during the critical rehabilitation period following ACL reconstruction.

All information will be logged into Red Cap.

B. Data Points

TSK and single leg balance on both sides will be measured by approved physical therapists.

C. Study Duration

The study is expected to collect and analyze data for 1-2 years.

D. Endpoints

Primary endpoints:

- TSK
- Single Leg Balance
- Strength as measured by MicroFET

Secondary endpoints:

- KOOS Jr.

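### Nothing keeps the TSK score from the therapist who times single-leg balance, so the study's one directional hypothesis is open to assessor expectation

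*Protocol*

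**What the plan says.** **Who measures.** Protocol 1.3B states: "TSK and single leg balance on both sides will be measured by approved physical therapists". Section 1.7 lists giving the TSK among the data-collection tasks and sets the place: "Data will be collected during physical therapy visits at the UOA research sites". Section 1.8 adds: "Single leg balance testing will be completed by physical therapists at 3 months, 6 months". At 6 months, under 1.3A, "all participants will undergo a functional evaluation by a physical therapist". The same part of 1.3A says that "strength testing will be conducted using the MicroFET device, with a focus on quadriceps and hamstrings at a 90-degree joint angle", and names no assessor for it.

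**Who acts on the TSK.** Section 4.6A says that fear and anxiety "will be assessed via the TSK (PROM) and patient concerned directly addressed by the physical therapists or referred for professional care".

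**How the TSK reaches the patient.** Section 1.8 has the pre-operative questionnaires sent by text or email. Section 4.6B has questionnaires completed online on a secure server.

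**What is being tested.** The hypothesis in 1.1B is that "patients who score higher on the TSK (more fear) will do worse on the single-leg balance test". Section 6.1 examines this by correlation at each time point, a longitudinal model, and a t-test by kinesiophobia status.

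**Masking.** None is described. The recording sheet in 4.6B carries only a patient number. That protects privacy but does not hide the TSK from the person filling in the sheet.

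**The concern.** In an association study, the exposure and the outcome should be measured so that knowledge of one cannot shape the other. Here one professional group is assigned to measure both, and is also expected to respond to the exposure. Its members know the study's purpose, because 4.1B and 4.4 have therapists explain it to patients and take consent. In 1.8, "Subjects are enrolled pre-surgically by physical therapist during pre-operative therapy".

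Time to touchdown is a fairly objective measure, but instruction, encouragement and the call on when the foot touches down all pass through the tester. Hand-held dynamometry depends on the examiner more. A tester who expects a fearful patient to balance badly can shift the result slightly without meaning to, and the shift is in the direction of the hypothesis. Such a shift would enter every analysis in 6.1 that relates TSK to balance. It could not be removed afterwards, because no analysis can restore masking that was not done.

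**Working it through.** The protocol states no figure on this point, so there is none to reproduce. The check is a comparison of sections, followed by an illustration of sensitivity.

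**Step 1. Does the balance tester have access to the TSK?**
- 1.3B and 1.7: therapists or team members measure or give the TSK. Read literally, the score is known.
- 1.8 and 4.6B: the patient completes questionnaires online. Read alone, the therapist need not see the score.
- 4.6A: therapists address what the TSK shows, so at some point they must know it.
- No section says when the score becomes visible relative to balance testing.

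Online completion limits a therapist's influence on the answers. It does not limit knowledge of the score.

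**Step 2. Do the two measurements coincide?** Sections 1.7 and 1.8 place the TSK before surgery and at 3, 6 and 12 months, and balance at 3 and 6 months. They coincide at 3 and 6 months, and the pre-operative score exists before the first balance test. Section 1.3A adds balance at 9 months and 1 year, but the two schedules do not. The point is therefore made for 3 and 6 months only.

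**Step 3. How sensitive is a study of this size?** Input from the protocol: N = 25 (1.5 and 4.3). Assumptions: no true association, two-sided 5% test, and an expectation effect of the sizes shown. The documents give none of these bias sizes.

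*Correlation, Fisher z.* Rejection probability = Φ(z − 1.96) + Φ(−z − 1.96), with z = atanh(r) × √(N − 3) and √22 = 4.690. The formula is symmetric in sign, and the hypothesised sign is negative.

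| Induced correlation (absolute) | z | Chance of p < 0.05 |
|---|---|---|
| 0 | 0 | 5% |
| 0.1 | 0.1003 × 4.690 = 0.47 | 7.6% |
| 0.2 | 0.2027 × 4.690 = 0.95 | 15.8% |
| 0.3 | 0.3095 × 4.690 = 1.45 | 30.6% |

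*Two-group t-test, noncentral t.* Noncentrality = shift / √(1/n1 + 1/n2). The group sizes are assumptions too.

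| Induced shift (SD) | 12 v 13 | 8 v 17 |
|---|---|---|
| 0.2 | 7.7% | 7.3% |
| 0.3 | 11.1% | 10.3% |
| 0.5 | 22.4% | 20.1% |

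These tables show what a given bias would do. They are not evidence that a bias of that size exists.

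**Step 4. Could adjustment for fear-directed care help?** Suppose, as an assumption, that such care went to everyone above the mean of a normally distributed TSK. The yes/no care variable would then correlate √(2/π) = 0.80 with the TSK, giving a variance inflation of 1 / (1 − 2/π) = 2.75. Such care also follows from the TSK, so adjusting for it conditions on a consequence of the exposure. It is not a suitable covariate for the main analysis.

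**The case against.** The strongest reply is that the protocol never says that one individual treats a patient, sees the score and tests that patient. Section 1.3B names a professional group, 1.5 lists four locations, and 1.7 speaks of specified team members. This is correct: the overlap is permitted, not prescribed. What stands is that nothing separates the roles or withholds the score.

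A second reply is that time to touchdown leaves little room for expectation. That bears on the size of the bias, which is unknown. It does not show that the bias is absent.

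A third is that masking within a visit is partial, since a therapist may remember an earlier score or earlier counselling. This also stands, and it limits what the fix can claim.

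A reader might infer more than the text supports:
- *Fear-directed care goes only to high scorers and cancels the association.* Section 4.6A gives no threshold, trigger or timing. Pre-operative TSK collection is standard of care under 1.7, so responding to fear may be part of the ordinary course that Objective 2 describes.
- *The result could not be attributed to kinesiophobia in either direction.* Section 1.1 asks about a relationship. The documents do not show that bias would overwhelm it.
- *Balance at 12 months is affected.* The schedules in 1.7 and 1.8 do not include that test.
- *Strength is certainly scored by the same therapist.* No assessor is named, and strength lies outside the stated hypothesis.

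A separate analysis plan would not answer the point, because who sees the score before testing is a matter of conduct.

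**Conclusion.** The point holds in a limited form. As written, the protocol lets the balance tester know the TSK score. Sections 1.3B, 1.7, 1.8 and 4.6 do not agree on who administers the TSK and who sees it. The hypothesis is directional, so the expected error favours it.

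The size of the bias is unknown. The figures of about 8% to 31% for the correlation, and about 7% to 22% for the t-test, rest on assumed bias, N = 25 and no true association. They should be read only as a sign that a study this small has little protection against a modest systematic shift. The change is worth making mainly because it is nearly free, not because large bias has been shown.

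**What to change.** 1. Reconcile 1.3B, 1.7, 1.8 and 4.6 so that they all say that the patient self-completes the TSK online, the route that 1.8 (for the pre-operative questionnaires) and 4.6B already describe.
2. State in 1.3B and 1.7 that the testing therapist does not see that visit's TSK score until the balance, hop and strength values for the visit are saved in REDCap. Where the recording sheet in 4.6B is used, its values should be entered before the score is released.
3. Release the score at the same visit, so that the response described in 4.6A is unchanged.
4. Optionally, add a dated yes/no REDCap field for fear-directed counselling or referral. None of the listed data items captures this, and the reporting route in 6.3 is for safety. Use the field for description only, not as a covariate in the main TSK-balance analysis.

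**Cost.** Protocol wording, a REDCap display setting and, if wanted, one field; no extra staff. The therapist sees the score slightly later in the visit. Scores remembered from earlier visits remain a residual source of bias, which the report should acknowledge.

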5.0 Special Considerations

5.1 Health Insurance Portability and Accountability Act (HIPAA)

N/A

5.2 Family Educational Rights and Privacy Act (FERPA)

N/A

5.3 Code of Federal Regulations Title 45 Part 46 (Vulnerable Populations)

N/A

5.4 General Data Protection Regulation (GDPR)

N/A

5.5 NJ Access to Medical Research Act (Surrogate Consent)

N/A

6.0 Data Management Plan

6.1 Data Analysis

Data will be analyzed using correlation testing—to test results at each time point—and longitudinal model—to show if there is a potential time effect on the results. Mean single-leg balance will be compared between time points based on whether the patient is diagnosed with kinesiophobia using a t-test. Power analysis via comparison to existing baseline values in the relevant literature was done to determine the number of participants required for a well-powered study.

6.2 Data Security

Patient information will be maintained on a password secured electronic record system.

6.3 Data and Safety Monitoring

A. Data/Safety Monitoring Plan

Periodic monitoring of patient safety will be maintained by the study coordinator. Any and all reported incidents, injuries or concerns will be promptly reported to the coordinator and PI. The study coordinator will report all issues to the IRB.

B. Data/Safety Monitoring Board Details

NA – Due to small numbers of study subjects (25) there is no need for a data monitoring committee.

6.4 Reporting Results

A. Individual Subjects' Results

Results of the study will be available to study participants at the conclusion of the study.

Therapists will discuss results of individual balance and functional testing with patients at completion of the testing.

B. Aggregate Results

Aggregate results will be available at the conclusion of the study for all participants.

C. Professional Reporting

Study results will be statistically analyzed and results compiled into a formal article which will be submitted for presentation/publication.

D. Clinical Trials Registration, Results Reporting and Consent Posting

NA

6.5 Secondary Use of the Data

Research will be saved for 5 years in a secure location at UOA. Use of de-identified data will be available to those who file formal request with purpose of use to PI/Study coordinator.

